## **Clinical Prediction Models for Pediatric In-Hospital Death Risk in Congolese Severe malaria Children Using Machine Learning Based-Algorithms**

### **I. FOCUS OF THE MANUSCRIPT**

Severe malaria (SM) is associated with a high risk of in-hospital death in resource-constrained countries. Improved risk-stratification methods can assist in referral decision-making and resource allocation. Investigators aim to 1) develop a prediction model for in-hospital death risk among children with severe malaria, compare its predictive performance to the current models, 2) validate previous models in our severe malaria population, and 3) assess the plasmodium-induced changes in clinical and biological parameters.

### **II. STUDY DESIGN**

- Type of study: Retrospective study of data collected prospectively during a period from January 30, 2017 to August 01, 2025.
- Study population: Children with severe malaria, admitted to the paediatric intensive care unit (PICU) of the Monkole Hospital Center (MHC) and the Kimbondo Pediatric Center (KPC), all in Kinshasa, DR.
- Inclusion criteria: Severe malaria children aged 2-9 years

### **III. STATISTICAL ANALYSIS PLAN**

#### **III.1. Descriptive statistics of the study population (Overall, Survivor and deceased children):**

##### Socio-demographic and anthropometric Data:

- Age
- Sex
- Geographical origin (district)

Data from Clinical Examination:

- Febrile episode
- Temperature
- Coma
- Blantyre coma scale
- Convulsions
- Pallor
- Jaundice
- Heart rate
- Respiratory rate
- Ketoacidosis respiration
- Hepatomegaly
- Splenomegaly
- Length of stay at PICU

Final Diagnoses and Antimalarial treatment

- Cerebral malaria
- Severe malaria Anaemia
- Severe respiratory malaria
- Antimalarial treatment using Artesunate
- Antimalarial treatment using Quinine

Laboratory Assessments

- PaCO2
- PaO2
- pH
- SBE
- Bicarbonate
- L-Lactate
- Glucose
- Potassium
- Sodium
- Calcium
- Magnesium
- Chlore
- Phosphore
- Blood urea nitrogen

- Creatinine
- Albumin
- Phosphate
- Hematocrit
- Total Bilirubin
- Parasitemia

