### III.2. Approaches by objectives

**Objective 1.** To develop a prediction model for in-hospital death risk among children with severe malaria

- Study population and inclusion criteria: Severe malaria children aged 2-9 years
- Outcome (dichotomous): Death during hospitalization (Survivors = 0, Deceased = 1). The end of hospitalization is defined as death (patients who died) or recovery (patients who survived), assessed up to 1-week post-admission.
- Predictors: Data from socio-demographic, anthropometric, clinical examination and laboratory Assessments.

**Objective 2.** To validate previous models in our severe malaria population

- Study population and inclusion criteria: Severe malaria children aged 2-9 years
- Primary Outcome: Death during hospitalization (Survivors = 0, Deceased = 1)
- Secondary Outcome: Time-to-risk event (risk event = death = 1 and censored event = Survival = 0). The end of hospitalization is defined as death (patients who died) or recovery (patients who survived), assessed up to 1-week post-admission.
- Predictors: Data from socio-demographic, anthropometric, clinical examination and laboratory Assessments.

**Objective 3.** To assess the plasmodium-induced changes in clinical and biological parameters.

- Study population and inclusion criteria: Severe malaria children aged 2-9 years
- Primary Outcome: Death during hospitalization (Survivors = 0, Deceased = 1)
- Secondary Outcome: Multiple organ dysfunction (MOD  $\geq$  2 organ systems fail)
- Predictor: Parasitemia

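### The Objective 1 predictor line, read with the plan's only list of its categories, does not exclude PICU length of stay, which is known only once the stay has ended

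*Combined protocol and SAP*

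**What the plan says.** Section III.2, Objective 1, gives the candidate predictors in one line: "Predictors: Data from socio-demographic, anthropometric, clinical examination and laboratory Assessments". It lists no variables, states no prediction time and names no exclusions.

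Section III.1, on descriptive statistics, is the only place where these categories are itemised. It has four blocks: socio-demographic and anthropometric, clinical examination, diagnoses and treatment, and laboratory. Under "Data from Clinical Examination" it lists 13 items, the last being "Length of stay at PICU".

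The Objective 1 outcome is death during hospitalization. The stay ends with death or recovery and is assessed up to one week after admission. Under Objective 2 the secondary outcome is "Time-to-risk event (risk event = death = 1 and censored event = Survival = 0". Section II describes the children as "admitted to the paediatric intensive care unit (PICU") at two centres. Section I gives the purpose: "Improved risk-stratification methods can assist in referral decision-making and resource allocation". It also says that the investigators will "compare its predictive performance to the current models".

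**The concern.** A completed PICU stay cannot be known when a prediction about that stay is needed. For a child who dies in the PICU, it is the time from PICU admission to death, which is close to what Objective 2 treats as an outcome. If the variable enters the Objective 1 model, two things follow.

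- The model cannot be applied to a new patient for the purposes in section I, however well it discriminates in the retrospective data.
- Stay may carry information about the outcome. If the current models do not use it (the documents do not name them), the planned comparison could be biased in favour of the new model.

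**Working it through.** The plan states no figure to reproduce. The main check is textual.

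**Step 1: set the two sections side by side.**

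| Block in III.1 | Named in the Objective 1 predictor line? |
|---|---|
| Socio-demographic and anthropometric | Yes |
| Clinical examination (13 items, the last being PICU length of stay) | Yes |
| "Final Diagnoses and Antimalarial treatment" | No |
| Laboratory | Yes |

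The line names three of the four blocks, in the order of III.1, and skips one. That fits a line written from those headings. The one visible omission is of a whole block, and it does not reach length of stay, which is filed under clinical examination.

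**Step 2: look for a rule that removes the variable.** There is no exclusion, no restriction to admission values, no prediction time and no screening step.

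**Step 3: ask when the variable is known.** It is known only when the PICU stay ends. Transfer to a ward before death or recovery does not change this, because the length of the PICU stay is still unknown at admission.

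**Step 4: illustrate the size.** The documents give no distribution of stay, mortality or AUC, so every input here is an assumption: log-normal stays with log-SD 0.7, survivors' median 4 days, admission-model AUC 0.80, and a deceased children's median of m days. Let r be the correlation, within outcome group, between the admission score and shorter stay.

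- d1 = √2 × z(0.80) = 1.414 × 0.8416 = 1.190
- d2 = ln(4/m)/0.7
- D² = (d1² + d2² − 2·r·d1·d2)/(1 − r²)
- combined AUC = Φ(D/√2)

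For m = 1 and r = 0: d2 = 1.386/0.7 = 1.980, D² = 1.417 + 3.922 = 5.339, D = 2.311, and AUC = Φ(1.634) = 0.949. For m = 2 and r = 0: d2 = 0.990, D² = 2.397, D = 1.548, and AUC = Φ(1.095) = 0.863.

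| m (days) | r = 0 | r = +0.3 | r = −0.3 |
|---|---|---|---|
| 1 | 0.949 | 0.929 | 0.973 |
| 2 | 0.863 | 0.832 | 0.904 |
| 3 | 0.813 | 0.800 | 0.845 |
| 4 | 0.800 | 0.811 | 0.811 |

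**Step 5: apply the one-week window.** The formula counts every death, whenever it occurs. On the most natural reading of III.2, only deaths by day 7 are events. This was simulated with 10% mortality (assumed), independence within outcome group, and a logistic model linear in log stay. Children dying after day 7 were treated as survivors censored at day 7.

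- m = 1: AUC rises from about 0.80 to 0.95.
- m = 2: from 0.798 to 0.872.
- m = 4: a change of about 0.01.
- m above 4: essentially no change.

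The last two results depend on the linear term. Under this rule a child whose stay reaches day 7 is a non-event by definition, so a more flexible algorithm could extract more.

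**The case against.** The strongest reply is that the defect is inferred, not written. A table split by survival normally reports length of stay, and III.1 is headed as descriptive. III.2 does not refer back to it. In ordinary usage, length of stay is not an examination finding, and the other 12 items in the block are signs, symptoms or vital signs. The skipped diagnoses-and-treatment block may even suggest that the authors meant to leave out what is not admission data. The consequences are also conditional: stay must be entered, and for the comparison the current models must lack it.

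Much of this stands. A reader might infer that the investigators intend to use length of stay as a predictor. The documents do not support that: no sentence says so, and a filing slip is plausible. What does not fall is the gap itself. III.1 is the only itemisation, the predictor line follows its headings, and nothing removes the variable.

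A reader might also infer a substantial gain if deceased children stayed longer than survivors. The Step 4 formula gives 0.825 and 0.863 for medians of 6 and 8 days at r = 0. Those values should not be used. Under the assumed distribution, the share of deaths after day 7 would be 1 − Φ(ln(7/6)/0.7) = 41% for a median of 6 days and 1 − Φ(ln(7/8)/0.7) = 58% for 8 days. Read naturally, the plan does not count those deaths as events.

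**Conclusion.** The point holds as a gap in the specification: taken literally, the Objective 1 predictor rule admits a variable known only after the PICU stay has ended. It does not show that such a model will be fitted. The case for correcting it rests on unusability at the time of prediction, which needs no numerical assumption, and on a conditional risk of bias in the model comparison.

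The illustration shows that inflation could be large when deaths come early and small when the two groups have similar stays. Its figures are neither estimates nor bounds. They rest on the assumed log-normal shape, log-SD, survivors' median, starting AUC and independence, on counting only deaths by day 7, and on a logistic model linear in log stay. Confidence is medium because the link between III.1 and III.2 is inferred.

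**What to change.** In section III.2, Objective 1, state that candidate predictors are limited to values available at the time of prediction (for example, PICU admission), and that PICU length of stay is excluded and kept as a descriptive variable only. Objective 2 carries the same predictor line, so the authors may wish to repeat the sentence there.

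The cost is one sentence and no new data. The reported AUC may be lower than it would be with stay included. If the listing was a filing slip, the same sentence settles it.

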### III.2. Approaches by objectives

**Objective 1.** To develop a prediction model for in-hospital death risk among children with severe malaria

- Study population and inclusion criteria: Severe malaria children aged 2-9 years
- Outcome (dichotomous): Death during hospitalization (Survivors = 0, Deceased = 1). The end of hospitalization is defined as death (patients who died) or recovery (patients who survived), assessed up to 1-week post-admission.
- Predictors: Data from socio-demographic, anthropometric, clinical examination and laboratory Assessments.

**Objective 2.** To validate previous models in our severe malaria population

- Study population and inclusion criteria: Severe malaria children aged 2-9 years
- Primary Outcome: Death during hospitalization (Survivors = 0, Deceased = 1)
- Secondary Outcome: Time-to-risk event (risk event = death = 1 and censored event = Survival = 0). The end of hospitalization is defined as death (patients who died) or recovery (patients who survived), assessed up to 1-week post-admission.
- Predictors: Data from socio-demographic, anthropometric, clinical examination and laboratory Assessments.

**Objective 3.** To assess the plasmodium-induced changes in clinical and biological parameters.

- Study population and inclusion criteria: Severe malaria children aged 2-9 years
- Primary Outcome: Death during hospitalization (Survivors = 0, Deceased = 1)
- Secondary Outcome: Multiple organ dysfunction (MOD  $\geq$  2 organ systems fail)
- Predictor: Parasitemia
